3.5 Purpose and timing of interim analyses/design adaptations

The primary endpoint analysis will be performed after all patients have completed the visit associated with the primary endpoint (Week 24). The interpretation of the MRI data will be performed by an imaging service provider and readers will be blinded to the treatment as well as visit information. The final analysis will be conducted after all patients have completed the study (Week 52). Additional analyses may be performed to support interactions with health authorities, as necessary.

3.6 Risks and benefits

Secukinumab is currently approved in Japan (since Dec 2014) for the treatment of PsA, as well as for the treatment of psoriasis vulgaris in adults not adequately responding to systemic therapies (except for biologics). Secukinumab is also approved in Europe (since Nov 2015) for the treatment of PsA and AS. Additionally, it is approved in Europe (since Jan 2015), the US (since Jan 2015) and Canada (since Mar 2015) for the treatment of moderate-to-severe plaque psoriasis.

As of July 2015, approximately 12 000 subjects have been enrolled in both completed and ongoing studies with secukinumab, with over 9 600 having received active drug at doses ranging from single and/or multiple doses of 0.1 mg/kg to 30 mg/kg i.v. and 25 mg to 300 mg s.c. across various indications (including psoriasis, RA, AS, PsA, multiple sclerosis and uveitis). Overall secukinumab was generally safe and well-tolerated.

The risk profile of secukinumab in AS and PsA is informed by the safety experience from psoriasis and arthritides trials. Secukinumab has been studied most extensively in psoriasis, and side effects seen in psoriasis patients treated with secukinumab include upper respiratory tract infections (nasopharyngitis, rhinitis) (very common: in more than 1 in 10 patients); oral herpes, rhinorrhea, diarrhea and urticaria (common: in more than 1 in 100 but fewer than 1 in 10 patients); oral candidiasis, tinea pedis, neutropenia, and conjunctivitis (uncommon: in more than 1 in 100 but fewer than 1 in 100 patients). Additionally, worsening of Crohn's disease, in some cases serious, was seen in studies of Crohn's disease and psoriasis, in patients

Novartis	Confidential	Page 29
Amended Clinical Trial Protocol \	/ersion 03 clean	Protocol No. CAIN457F3301

receiving secukinumab or placebo. Immunogenicity was low with secukinumab and did not correlate with hypersensitivity-related AEs or loss of efficacy in any of the indications studied to date. No new or unexpected safety signals were detected in any AS and PsA study for any dose regimen and the safety profile in this patient population was consistent with the safety profile observed in other indications including psoriasis.

The risk to patients in this trial will be minimized by compliance with the eligibility criteria, close clinical monitoring and extensive guidance to the investigators, provided in the current version of the investigator brochure (IB).

4 Population

The study population will consist of male and female patients (\geq 18 years old at the time of consent) with active PsA or axSpA presenting active enthesitis including one Achilles tendon site that is refractory to standard treatment as defined in Section 4.1 and Section 4.2.

4.1 Inclusion criteria

Patients eligible for inclusion in this study must fulfill all of the following criteria:

- 1. Patient must be able to understand and communicate with the investigator and comply with the requirements of the study and must provide written, signed and dated informed consent before any study assessment is performed.
- 2. Male or non-pregnant, non-lactating female patients at least 18 years of age.
- 3. PsA patients must fulfill the following criteria:
 - Diagnosis of PsA classified by CASPAR criteria with symptoms for at least 6 months (Appendix 3) and
 - Active PsA as assessed by ≥ 1 tender joints out of 78 and ≥ 1 swollen joints out of 76 at Baseline (dactylitis of a digit counts as 1 joint each).
- 4. AxSpA patients must fulfill the following criteria:
 - AxSpA as per the classification of the ASAS axial SpA criteria (Appendix 4) with objective signs of inflammation at screening, evident by either MRI with Sacroiliac joint inflammation or definite radiographic sacroilitis according to the modified New York criteria (Appendix 5) (both according to source documentation) and/or hsCRP > ULN (as defined by central lab) and
 - Active disease assessed by total BASDAI \geq 4 (0-10) (Appendix 6) at Baseline.
- 5. Diagnosis of Achilles tendon enthesitis according to swelling and tenderness at the insertional site of the Achilles tendon into the calcaneus.
- 6. Onset of heel pain ≥ 1 month at Baseline.
- 7. Heel enthesitis that is MRI-positive according to the investigator's judgement.
- 8. The heel enthesitis must have been refractory to standard treatment defined as either NSAIDs for at least 1 month at the maximal recommended or tolerated dose unless withdrawal because of intolerance, toxicity or contraindications or TNF-inhibitors as described in inclusion criterion 16.
- 9. Rheumatoid factor (RF) and anti-cyclic citrullinated peptide (anti-CCP) antibodies negative at Screening.
- 10. Patients should have been on NSAIDs at the highest recommended dose for at least 1 month prior to randomization with an inadequate response or failure to respond, or less if

therapy had to be withdrawn due to intolerance, toxicity or contraindications or on TNF-inhibitors as described in inclusion criterion 16.

- 11. Patients who are regularly taking NSAIDs as part of their PsA or axSpA therapy are required to be on a stable dose for at least 2 weeks before study randomization and should remain on a stable dose up to Week 24.
- 12. Patients taking corticosteroids must be on a stable dose of ≤ 10 mg/day prednisone or equivalent for at least 2 weeks before randomization and should remain on a stable dose up to Week 24.
- 13. Patients taking MTX (7.5 mg/week to 25 mg/week) or only in case of axSpA sulfasalazine (≤ 3 g/day) are allowed to continue their medication and must have taken it for at least 3 months and have to be on a stable dose for at least 4 weeks prior to randomization and should remain on a stable dose up to Week 24.
- 14. Patients on MTX must be on folic acid supplementation at randomization.
- 15. Patients who are on a DMARD other than MTX or only in case of axSpA sulfasalazine must discontinue the DMARD 4 weeks prior to randomization, except for leflunomide, which has to be discontinued for 8 weeks prior to randomization unless a cholestyramine washout has been performed.
- 16. Patients who have been on a TNFα inhibitor (not more than two) must have experienced an inadequate response to previous or current treatment given at an approved dose for at least 3 months prior to randomization or have been intolerant to at least one administration of an anti-TNFα agent
- 17. Patients who have previously been on a TNFα inhibitor will be allowed entry into study after an appropriate wash-out period prior to randomization:
 - 4 weeks for etanercept with a terminal half-life of 102 ± 30 hours (s.c. route)
 - 8 weeks for infliximab with a terminal half-life of 8.0-9.5 days (i.v. infusion)
 - 10 weeks for adalimumab with a terminal half-life of 10-20 days (average 2 weeks) (s.c. route)
 - 10 weeks for Simponi[®] (golimumab) with a terminal half-life of 11-14 days
 - 10 weeks for Cimzia® (certolizumab) with a terminal half-life of 14 days

4.2 Exclusion criteria

Patients fulfilling any of the following criteria are not eligible for inclusion in this study. No additional exclusions may be applied by the investigator, in order to ensure that the study population will be representative of all eligible patients.

- 1. Chest X-ray or chest MRI with evidence of ongoing infectious or malignant process obtained within 3 months prior to screening and evaluated by a qualified physician.
- 2. Patients taking high potency opioid analgesics (e.g. methadone, hydromorphone, morphine).
- 3. Previous exposure to secukinumab or other biologic drug directly targeting IL-17 or IL-17 receptor.
- 4. Use of any investigational drug and/or devices within 4 weeks before randomization or a period of 5 half-lives of the investigational drug, whichever is longer.
- 5. Ongoing use of psoriasis treatments / medications (e.g. topical corticosteroids, UV therapy) at randomization. The following wash out periods need to be observed:

- Oral or topical retinoids: 4 weeks.
- Photochemotherapy (e.g. PUVA): 4 weeks.
- Phototherapy (UVA or UVB): 2 weeks.
- Topical skin treatments (except in face, eyes, scalp and genital area during screening, only corticosteroids with mild to moderate potency): 2 weeks.
- 6. History of hypersensitivity to any of the study drugs or its excipients or to drugs of similar chemical classes.
- 7. Any intramuscular or intravenous corticosteroid treatment within 4 weeks before randomization.
- 8. Any therapy by intra-articular injections (e.g. corticosteroid) within 4 weeks before randomization.
- 9. Patients who have previously been exposed to more than two (2) TNF inhibitors (investigational or approved).
- 10. Patients who have ever received biologic immunomodulating agents, except those targeting $TNF\alpha$.
- 11. Previous treatment with any cell-depleting therapies including but not limited to anti-CD20, investigational agents (e.g. Campath, anti-CD4, anti-CD5, anti-CD3, anti-CD19).
- 12. Pregnant or nursing (lactating) women, where pregnancy is defined as the state of a female after conception and until the termination of gestation, confirmed by a positive human chorionic gonadotropin (hCG) laboratory test.
- Women of child-bearing potential, defined as all women physiologically capable of becoming pregnant, unless they are using effective methods of contraception during dosing of study treatment and minimum 16 weeks or longer if local label requires it (e.g. 20 weeks in EU) after stopping the study medication. Effective contraception methods include:
 - Total abstinence (when this is in line with the preferred and usual lifestyle of the subject). Periodic abstinence (e.g., calendar, ovulation, symptothermal, post-ovulation methods) and withdrawal are not acceptable methods of contraception
 - Female sterilization (have had surgical bilateral oophorectomy with or without hysterectomy) total hysterectomy or tubal ligation at least 6 weeks before taking investigational drug. In case of oophorectomy alone, only when the reproductive status of the woman has been confirmed by follow up hormone level assessment
 - Male sterilization (at least 6 months prior to screening). For female subjects on the study, the vasectomized male partner should be the sole partner for that subject
 - Barrier methods of contraception: condom or occlusive cap (diaphragm or cervical/vault caps) with spermicidal foam/gel/film/cream/ vaginal suppository.
 - Use of oral, (estrogen and progesterone), injected or implanted hormonal methods of contraception or placement of an intrauterine device (IUD) or intrauterine system (IUS) or other forms of hormonal contraception that have comparable efficacy (failure rate <1%), for example hormone vaginal ring or transdermal hormone contraception

In case of use of oral contraception women should have been stable on the same pill for a minimum of 3 months before taking investigational drug.

Women are considered post-menopausal and not of child bearing potential if they have had 12 months of natural (spontaneous) amenorrhea with an appropriate clinical profile (e.g. age

appropriate, history of vasomotor symptoms) or have had surgical bilateral oophorectomy (with or without hysterectomy), total hysterectomy or tubal ligation at least 6 weeks ago. In the case of oophorectomy alone, only when the reproductive status of the woman has been confirmed by follow up hormone level assessment is she considered not of child bearing potential.

- 14. Active ongoing inflammatory diseases other than PsA and axSpA that might confound the evaluation of the benefit of secukinumab therapy, including inflammatory bowel disease or uveitis.
- 15. Underlying metabolic, hematologic, renal, hepatic, pulmonary, neurologic, endocrine, cardiac, infectious or gastrointestinal conditions which in the opinion of the investigator immunocompromises the patient and/or places the patient at unacceptable risk for participation in an immunomodulatory therapy.
- 16. Significant medical problems or diseases, including but not limited to the following: uncontrolled hypertension (≥ 160/95 mmHg), congestive heart failure (New York Heart Association status of class III or IV), and uncontrolled diabetes.
- 17. History of clinically significant liver disease or liver injury as indicated by abnormal liver function tests (LFT) such as aspartate aminotransferase/serum glutamic oxaloacetic transaminase (AST/SGOT), alanine aminotransferase/ serum glutamic pyruvic transaminase (ALT/SGPT), alkaline phosphatase, or serum bilirubin. The investigator should be guided by the following criteria:
 - Any single parameter may not exceed 2 × ULN. A single parameter elevated up to and including 2 × ULN should be re-checked once more as soon as possible, and in all cases, at least prior to enrollment/randomization, to rule out laboratory error.
 - If the total bilirubin concentration is increased above $2 \times ULN$, total bilirubin should be differentiated into the direct and indirect reacting bilirubin. In any case, serum bilirubin should not exceed the value of 1.6 mg/dL (27 μ mol/L).
- 18. History of renal trauma, glomerulonephritis, or patients with 1 kidney only, or a serum creatinine level exceeding 1.5 mg/dL (132.6 μmol/L).
- 19. Screening total white blood cell (WBC) count < 3000/μL, or platelets < 100000/μL or neutrophils < 1,500/μL or hemoglobin < 8.5 g/dL (85 g/L).
- 20. Active systemic infections during the last 2 weeks (exception: common cold) prior to randomization.
- 21. History of ongoing, chronic or recurrent infectious disease or evidence of tuberculosis infection as defined by a positive QuantiFERON TB-Gold test. Patients with a positive test may participate in the study if further work up (according to local practice/guidelines) establishes conclusively that the patient has no evidence of active tuberculosis. If presence of latent tuberculosis is established then treatment according to local country guidelines must have been initiated.
- 22. Known infection with human immunodeficiency virus (HIV), hepatitis B or hepatitis C at screening or randomization.
- 23. History of lymphoproliferative disease or any known malignancy or history of malignancy of any organ system within the past 5 years (except for basal cell carcinoma or actinic keratoses that have been treated with no evidence of recurrence in the past 3 months, carcinoma in situ of the cervix or non-invasive malignant colon polyps that have been removed).

- 24. Current severe progressive or uncontrolled disease which in the judgment of the clinical investigator renders the patient unsuitable for the trial.
- 25. Inability or unwillingness to undergo repeated venipuncture (e.g. because of poor tolerability or lack of access to veins).
- 26. Any medical or psychiatric condition which, in the investigator's opinion, would preclude the participant from adhering to the protocol or completing the study per protocol.
- 27. Donation or loss of 400 mL or more of blood within 8 weeks before randomization.
- 28. History or evidence of ongoing alcohol or drug abuse, within the last 6 months before randomization.
- 29. Plans for administration of live vaccines during the study period or within 6 weeks preceding randomization.
- 30. Inability or unwillingness to undergo MRI of the feet (e.g., patients with pacemakers, or metal fragments / foreign objects in the body that are not compatible with performing an MRI of the feet)

5 Treatment

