Enthesitis is a frequent manifestation in PsA and SpA and approximately 40% of patients with SpA have enthesitis (Haibel and Sieper 2015). The main clinical manifestations of enthesitis are represented by pain and swelling at the entheseal sites. The pain, in particular, may be severe, persistent and resistent to treatment (D'Agostino et al 2002). Enthesitis is represented by inflammation at the enthesis, which is an anatomical area where ligaments, tendons and joint capsules attach to the bone (D'Agostino and Olivieri 2006). Enthesitis can occur at any site but most frequently localizes in the heel at the 'premiere enthesis', the Achilles tendon (D'Agostino and Olivieri 2006, Haibel and Sieper 2015, D'Agostino et al 2002). In terms of diagnosing enthesitis differential diagnosis should be considered, e.g. mechanical-degenerative causes and fibromyalgia (Haibel and Sieper 2015). Therefore a straightforward approach combining physician-based assessment of Achilles tendon enthesitis with patient-reported outcomes and imaging techniques such as magnetic resonance imaging (MRI) would be the most reliable and appropriate (D'Agostino and Olivieri 2006).

The therapeutic options for enthesitis are limited since only a small number of controlled trials have been performed to date. Non-steroidal anti-inflammatory drugs (NSAID) and local injections of corticosteroids are recommended for treatment of enthesitis although efficacy has only been reported in case studies (Zochling et al 2006, Ritchlin et al 2009). In patients with refractory enthesitis therapeutic approach using NSAIDs, physiotherapy or steroid injections are often not sufficient (D'Agostino et al 2002). For disease modifying anti-rheumatic drugs (DMARD) no efficacy could be demonstrated in small open-label clinical trials (Haibel et al 2005, Haibel et al 2007). Treatment efficacy in PsA/AS associated enthesitis with anti-TNF therapy has been shown using composite indices in clinical trials investigating the overall efficacy, tolerability and safety of anti-TNF α agents in PsA/AS (Kavanaugh et al 2009, Mease et al 2014, van der Heijde et al 2006). A randomized, doubleblind, placebo-controlled interventional proof-of-concept trial specifically dedicated to enthesitis has been performed only by one compound so far (Dougados et al 2010). In this

Novartis	Confidential	Page 21
Amended Clinical Trial Protocol Version 0)3 clean	Protocol No. CAIN457F3301

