5.5.7 Concomitant medication

The investigator must instruct the patient to notify the study site about any new medications he/she takes after the patient was enrolled into the study. All medications, procedures and significant non-drug therapies (including physical therapy and blood transfusions) administered after the patient was enrolled into the study must be recorded in the concomitant medications/significant non-drug therapies eCRF.

Each concomitant drug must be individually assessed against all exclusion criteria/prohibited medication. If in doubt the investigator should contact the Novartis medical monitor before randomizing a patient or allowing a new medication to be started.

Novartis	Confidential	Page 40
Amended Clinical Trial Protocol Version	03 clean	Protocol No. CAIN457F3301

The effect of secukinumab on live vaccines is unknown; therefore live vaccines should not be administered during participation in the study. In case a live vaccine has been administered due to a medical urgency, study treatment should be interrupted for 12 weeks.

Guidelines for the use of specific medications are provided below:

Methotrexate

Patients taking MTX (up to 25 mg/week) must be on a stable dose for at least 4 weeks before randomization and maintained stable until Week 24.

Folic acid

Patients on MTX must be taking folic acid supplementation at randomization and during the trial to minimize the likelihood of MTX associated toxicity.

Sulfasalazine

Patients taking sulfasalazine (≤ 3 g/day) must be on a stable dose for at least 4 weeks before randomization and maintained stable until Week 24. Any changes in dose or initiation after Week 24 must be recorded in the Prior/Concomitant medications eCRF page.

Leflunomide wash-out with cholestyramine

In case of leflunomide treatment, a drug wash-out of 8 weeks has to be performed. However, another wash-out procedure might be considered. Cholestyramine could be given orally to wash-out the drug at a dose of 8 g t.i.d. Cholestyramine has been shown to reduce plasma levels of the active leflunomide metabolite by approximately 40% in 24 hours and by 49% to 65% in 48 hours in 3 healthy volunteers. The administration of cholestyramine is recommended in patients who require a drug elimination procedure. If a patient receives 8 g t.i.d. for 11 days he/she could be safely randomized 4 weeks after the beginning of the 11-day treatment period.

Systemic corticosteroids

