Treatment with systemic corticosteroids is permitted up to a maximum daily dosage of ≤ 10 mg prednisone equivalent and if the dose was stable within the 2 weeks preceding randomization. The patient should remain on a stable dose until Week 24.

Corticosteroid dose reductions below 10 mg prednisone equivalent are permitted after Week 24 although the corticosteroid dose should not be reduced more than 1 mg prednisone equivalent every 4 weeks.

Any change in the dose of systemic corticosteroids during the trial must be recorded on the corresponding eCRF page.

Intra-articular corticosteroids are not permitted within the 4 weeks preceding randomization and up to Week 24. After Week 24, no more than 1 joint per 24-week period may be injected. No single injection should exceed 40 mg of triamcinolone (or equivalent) and the total dose of intra-articular corticosteroid may not exceed 80 mg of triamcinolone (or equivalent) during any 52-week period.

Non-steroidal anti-inflammatory drugs (including COX-1 or COX-2 inhibitors), low strength opioids and acetaminophen/paracetamol

Patients should have been on NSAIDs at the highest recommended dose for at least 1 month prior to randomization with an inadequate response or failure to respond, or less if therapy had to be withdrawn due to intolerance, toxicity or contraindications.

Patients regularly using NSAIDs, low strength opioids, or paracetamol/acetaminophen should be on stable dose for at least 2 weeks before randomization to allow inclusion. They should remain on a stable dose in the study up to Week 24. However, they have to refrain from any intake during at least 24 hours before a visit with disease activity assessment.

After Week 24 assessments are completed, a change in the NSAIDs, low strength opioids, or paracetamol/acetaminophen treatment regimen as well as PRN use are permitted.

Any change of the NSAIDs, low strength opioids, or paracetamol/acetaminophen treatment during the trial should be recorded in the Prior/Concomitant medications eCRF page.

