5.5.8 Prohibited medication

Use of the treatments displayed in Table 5-1 is NOT allowed after the start of the washout period.

Live vaccines should not be given until 12 weeks after last study treatment administration.

Prohibited medication	Washout period (before randomization)
Etanercept*	4 weeks
Infliximab*	8 weeks
Adalimumab, golimumab, certolizumab*	10 weeks
Biological immunomodulating agents* except TNF inhibitors as described above	Never
Unstable dose of MTX or sulfasalazine (until Week 24)	4 weeks
Other DMARD (incl. apremilast, except MTX and – in case of axSpA - sulfasalazine)	4 weeks
Leflunomide	8 weeks
Leflunomide with cholestyramine washout	4 weeks
Unstable doses of NSAIDs (COX1 or COX2 inhibitors), low strength opioids, paracetamol/acetaminophen (until Week 24). After week 24, use PRN is allowed.	2 weeks
Analgesics, other than NSAIDs or paracetamol/acetaminophen or low strength opioids as described above	2 weeks
Systemic corticosteroids > 10 mg prednisone equivalent** (until Week 52)	2 weeks
Unstable dose of systemic corticosteroids \leq 10 mg prednisone equivalent (until Week 24)	2 weeks
Intra-articular injections (until Week 24)	4 weeks
Intramuscular or intravenous corticosteroid treatment	4 weeks
Any cell-depleting therapies including but not limited to anti-CD20 or investigational agents (e.g., CAMPATH, anti-CD4, anti-CD5, anti-CD3, anti-CD19)	Never
Any investigational treatment or participation in any interventional Trial	4 weeks or 5 half-lives (whichever is longer)

Table 5-1	Prohibited	medication

Prohibited medication	Washout period (before randomization)
Live vaccines (and until 12 weeks after last study treatment administration, see above)	6 weeks
Oral or topical retinoids	4 weeks
Photochemotherapy (e.g. PUVA)	4 weeks
Phototherapy (UVA or UVB)	2 weeks
Topical skin treatments (except in face, eyes, scalp and genital area during screening, only corticosteroids with mild to moderate potency)	2 weeks

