of $\geq 20\%$ [PsA patients]) or BASDAI of $\geq 20\%$ or ≥ 1 unit (0-10 scale) (axSpA patients, Pavy et al 2005) at Week 36 may be considered as a guidance for considering a patient inadequate responder to secukinumab treatment.

For patients who discontinue study treatment, a Dosage Administration Record eCRF should be completed, giving the date and primary reason for stopping study treatment.

The investigator must also contact the IRT to register the patient's discontinuation from study treatment.

If study drug discontinuation occurs because the treatment code has been broken, please refer to Section 5.5.9.

Patients who prematurely discontinue during Treatment Period 1 (secukinumab/placebo treatment from Baseline through Week 24) should return for assessments associated with Week 24 visit (4 weeks after the last study treatment in Treatment Period 1). Patients who prematurely discontinue during Treatment Period 2 (secukinumab treatment from Week 24 through Week 52) should return and complete assessments associated with Week 52 visit (4 weeks after the last study treatment in Treatment Period 2, see Table 6-1). The final visit should be performed before any new treatment is initiated.

Patients who prematurely withdraw from the study will not be replaced.

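### The injection limits name only intra-articular injections, so a local steroid injection at the study heel has no washout and is not on the prohibited list; the effect is probably small and towards no difference

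*Protocol*

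**What the plan says.** **Injection limits.** Three places restrict local injections. Exclusion 8 excludes "Any therapy by intra-articular injections (e.g. corticosteroid) within 4 weeks before randomization". Protocol Section 5.5.7 says "Intra-articular corticosteroids are not permitted within the 4 weeks preceding randomization and up to Week 24". Table 5-1 (Section 5.5.8) has a matching row for intra-articular injections, with a 4-week washout and a ban to Week 24. Exclusion 7 and another Table 5-1 row cover intramuscular and intravenous steroid. Inclusion 12 and Section 5.5.7 cover stable daily doses.

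**Place of local injection.** Section 1.1 states that "local injections of corticosteroids are recommended for treatment of enthesitis although efficacy has only been reported in case studies".

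**Discretion.** Section 4.2 does not let investigators add exclusions. Section 5.5.7 has each drug checked against the exclusions and the prohibited list, and adds: "If in doubt the investigator should contact the Novartis medical monitor before randomizing a patient or allowing a new medication to be started".

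**Rescue.** Section 5.5.6 forbids rescue medication until the Week 24 assessments are complete, and discontinues patients rescued with treatments described in Section 5.5.8. Section 3.1 speaks only of prohibited biologics there, and places discontinuation after an end-of-study visit.

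**Counting.** The primary endpoint is resolution of Achilles enthesitis on the LEI, which records tenderness as present or absent, at Week 24 in the FAS. Under Protocol 9.4.3 and SAP 2.5.3, a patient with a missing assessment is a responder if the criterion was met at drop-out. SAP Table 5.1-4 keeps patients with rescue use (OTH03) and with prohibited medication (COMD01) in every analysis set.

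**The concern.** The trial treats one tendon insertion, yet its injection rules are written for joints. A patient could have the study heel injected days before Baseline and, if still eligible on examination, be randomized with no criterion breached. Some Week 24 resolutions could then owe something to the steroid. In both arms this adds responses unrelated to the assigned treatment.

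The second matter is on-study use. A heel injection for symptoms before Week 24 is a breach, but nothing visible in the plan stops a heel that becomes non-tender afterwards from counting as a response to the assigned arm. If such injections are commoner on placebo, the contrast shrinks. At stake are some power and a clean reading of the response rates.

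**Working it through.** **1. Is a heel injection caught anywhere before randomization?**
- Exclusion 8, Section 5.5.7 and Table 5-1: intra-articular only. The enthesis, the peritendinous tissue and the bursa are not the joint.
- Exclusion 7: intramuscular and intravenous only.
- Inclusion 12: "Patients taking corticosteroids must be on a stable dose of ≤ 10 mg/day prednisone or equivalent for at least 2 weeks before randomization". No route is named, but the wording describes a daily dose and does not fit a single local injection.
- Medical monitor: consulted only in case of doubt; no interval is set.

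So no washout exists for this injection.

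**2. What limits the effect?** Inclusion 5 requires "Diagnosis of Achilles tendon enthesitis according to swelling and tenderness at the insertional site of the Achilles tendon into the calcaneus". Eligibility is checked and the LEI done at Screening and Baseline (Table 6-1 and footnote b), so a heel that has settled by Baseline should fail. Inclusions 7 and 8 add MRI positivity and refractoriness. The only pre-treatment foot MRI is at Screening, up to 10 weeks earlier, so a later injection leaves inclusion 7 satisfied. The washout also buys little time: an injection 2 weeks before Baseline is 26 weeks before the endpoint, against at least 28 with the 4-week rule.

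**3. What happens to a patient injected in breach before Week 24?**
- Stays: the observed Week 24 tenderness is used. Section 5.5.6 ties discontinuation to Section 5.5.8, where this injection is absent.
- Is discontinued because of the injection: the end-of-study visit follows the injection, and status at drop-out is carried. Section 5.6.2 says "The final visit should be performed before any new treatment is initiated", but that protects patients who stop first and are treated later.

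Either way a non-tender heel counts as a response. An intra-articular injection, which is listed, has the same outcome, so this does not come from the wording of exclusion 8.

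**4. The plan's own figure.** Protocol 9.8: 45% versus 21%, two-sided 5%, 90% power, 89 per arm. The normal approximation gives 79 per arm, or 87 with continuity correction; Fisher's exact test at 89 per arm has 91.0% power. The figure is reproduced closely enough. At 100 per arm Fisher power is 94.0%.

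**5. Injection before Baseline.** Assumptions, none from the documents: share f injected in each arm (5% or 10%); injected placebo patients resolve at r = 30%, 50% or 70%; injected patients keep a share k of the 24-point effect.

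p0 = (1−f)×0.21 + f×r; p1 = (1−f)×0.45 + f×(r + k×0.24); difference = 0.24×(1 − f×(1−k)).

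Example, f = 10%, r = 50%, k = 0: p0 = 0.189 + 0.050 = 0.239; p1 = 0.405 + 0.050 = 0.455; difference 0.216; power 87.0%.

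| k | f | Difference (points) | Fisher power, 100 per arm (r = 30/50/70%) |
|---|---|---|---|
| 1 | 5% | 24.0 | 93.8 / 93.4 / 93.1% |
| 1 | 10% | 24.0 | 93.6 / 92.9 / 92.4% |
| 0.5 | 5% | 23.4 | 92.7 / 92.3 / 91.9% |
| 0.5 | 10% | 22.8 | 91.2 / 90.3 / 89.6% |
| 0 | 5% | 22.8 | 91.5 / 90.9 / 90.5% |
| 0 | 10% | 21.6 | 88.2 / 87.0 / 86.1% |

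**6. Breach before Week 24 (scale only).** One or two net extra placebo responders per 100, with secukinumab at 45%: 45% versus 22% gives 91.6%; 45% versus 23% gives 88.6% (Fisher). More severely, let a share f of placebo non-responders be injected and all resolve: placebo rate = 0.21 + 0.79×f, so 22.6%, 25.0% or 28.9% for f = 2%, 5% or 10%. Uncorrected power at 100 per arm falls from 95.6% to 92.4%, 85.0% or 65.7%. If secukinumab non-responders are injected at half that rate and all resolve, it is 93.5%, 89.1% or 78.7%.

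**The case against.** The strongest reply is that this hardly matters. A still swollen and tender heel at Baseline has not responded to any recent injection, and two extra weeks of distance from a Week 24 endpoint change little. All the rates above are assumed. Rescue is banned; SAP 2.3.1 expects rescued patients to have discontinued; medications and procedures are recorded, so cases would be visible. Analysing observed status as randomized follows the intent-to-treat principle and is conservative here. All of this stands, and it sets the weight. It does not supply a washout, and discontinuing the patient does not remove the response.

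A reader might infer more than the documents support:
- *That heel injections are allowed on study.* They are not, when given for symptoms: Section 5.5.6 bars them as rescue.
- *That the gap could produce a false superiority claim.* Injections before Baseline are balanced in expectation by randomization and dilute the contrast unless injected patients gain more from the drug than others. Breach injections more common on placebo also pull towards no difference.
- *That listing the injection, or aligning Section 3.1 with Section 5.5.6, closes the counting problem.* Neither does; the patient would leave and still be counted.
- *That the plan has no analysis for rescue.* The SAP contents show a blacked-out entry directly after 2.5.3, so this cannot be known.

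**Conclusion.** The omission is real. A local entheseal, peritendinous or bursal steroid injection at the study heel has no washout and is not on the prohibited list, in a trial whose endpoint is that site. Its effect through injections before Baseline is probably small: power falls clearly below 90% only if 10% are injected and the drug does nothing in them.

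The counting of breach injections is a separate matter, common to all rescue medication. It stays small as long as breaches are rare, as the ban intends; the larger losses above need 5 to 10% of placebo non-responders to be injected and all to resolve, which nothing in the documents suggests. The rates are assumptions throughout, and Fisher or normal-approximation power stands in for the planned logistic model. The point is of low weight and does not threaten the primary conclusion.

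**What to change.** 1. In exclusion 8, the Section 5.5.7 sentence and the Table 5-1 row, extend the limit to intra-articular or local heel (entheseal, peritendinous, bursal) injections, with the same 4-week washout and ban until Week 24. Cost: a few words in three places, and a few patients delayed at screening by up to 4 weeks.

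2. Unless the redacted SAP entry after 2.5.3 already does so, add one sensitivity analysis of the primary endpoint that counts patients injected in the study heel before Week 24, completers and drop-outs alike, as non-responders. Record the side injected; code OTH03 helps to find the cases. Cost: one data item and one table.

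Keep the primary analysis and the FAS unchanged. If injections are commoner on placebo, the non-responder rule could favour secukinumab, so it belongs in a sensitivity analysis only.
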